Abbreviations: AE=adverse event; C=Cycle; CGIC=clinician global impression of change; CGIS=clinician global impression of severity; D/d=(D)day(s); ECG=electrocardiogram; EOT=End-of-Treatment; MRI=magnetic resonance imaging; PE=physical examination; PF=Physical Function; PK=pharmacokinetics; ROM=range of motion; SAE=serious adverse event; TGCT=tenosynovial giant cell tumor; W=week; w/in=within.

^a EOT assessments do not need to be repeated if the assessment was done within the previous 7 days.

^b The Safety Follow-up Visit should be conducted 30 days (±5 days) after the last dose of study drug or prior to the initiation of any new TGCT therapy and/or surgery, whichever comes first. If a participant has been off study drug for more than 30 days at the time of decision to stop treatment, then the Safety Follow-up Visit will be conducted at the EOT visit. Information about new TGCT therapy and/or surgery will be collected during Safety Follow-up.

^c Disease follow-up will begin 12 weeks (±4 weeks) after last dose of study drug and an MRI will be required at this visit. All subsequent disease follow-up will be conducted by telephone every 16 weeks (±4 weeks) and a review of the participant's medical records for disease status changes will be performed. Disease follow-up will continue for up to 2 years after last dose of study drug, or until disease progression, withdrawal of consent, or start of new TGCT therapy and/or surgery, whichever occurs first. Participants who discontinue study due to confirmed disease progression by IRR will not need to complete Disease Follow-up Visit. Any SAE occurring during this follow-up period must be reported if assessed as related to study drug by the Investigator.

visits, participants may dose at home.

- ^d For conduct of End of Part 1 visit assessments refer to Section 11.5.1. Assessments from End of Part 1 will serve as C1D1 crossover assessments for C1D1 CO (ie, baseline assessments) and C7D1 assessments for participants continuing on study drug in Part 2. Participants continuing to Part 2 (open
- label) should follow assessment schedule in Table 2 and Table 3, as applicable, after all required blinded assessments are completed.
- ^e Histological confirmation of TGCT diagnosis is required for eligibility. Refer to Section 11.9.2 for more information.

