7. INVESTIGATIONAL PLAN

7.1. Overall Study Design

This is a multicenter, randomized, placebo-controlled study of vimseltinib in patients with TGCT, consisting of 2 parts: Part 1 is double-blinded and Part 2 is open label. Symptomatic patients with histologically confirmed TGCT for whom surgical resection will potentially cause worsening functional limitation or severe morbidity will be eligible. Patients who received anti-CSF1/CSF1R therapy previously (except for imatinib or nilotinib) will be excluded. The study will evaluate efficacy, safety, clinical outcome assessments, PK, and pharmacodynamics of vimseltinib in this population.

The study will consist of a 42-day screening period prior to the first dose of study drug, a Part 1 double-blinded treatment period of 24 weeks (referred to in 28-day cycles) and a Part 2 open-label period until Week 49 (Figure 1). Participants will continue treatment after Week 49 during the extension period. There will also be an End-of-Treatment (EOT) Visit within 7 days after the decision to stop study drug, a Safety Follow-up Visit 30 days (\pm 5 days) after the last dose of study drug, and a Disease Follow-up period of up to 2 years or until initiation of new TGCT treatment or surgery, whichever occurs first. A summary of visit flow is provided in Figure 2. Participants will be allowed to undergo surgical resection only after completion of Part 1.

Approximately 120 participants will be randomized in a 2:1 ratio to receive either vimseltinib at the dose of 30 mg twice weekly (biw) (n=80) or placebo (n=40) for 24 weeks. Randomization will be stratified for tumor location (lower limb/all other) and region (U.S./non-U.S.).

At Week 25, the primary and secondary endpoints will be assessed, and participants randomized to placebo in Part 1 will have the option to crossover and receive open-label vimseltinib in Part 2 upon completion of Part 1. Participants randomized to placebo in Part 1 with confirmed disease progression by blinded IRR before Week 25 are eligible for early entry into Part 2. Participants randomized to vimseltinib in Part 1 with confirmed disease progression by IRR before Week 25 will discontinue from study, while those without confirmed disease progression by IRR before Week 25 will continue to receive vimseltinib in Part 2 upon completion of Part 1.

[figure not shown]

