9.4.1. Blinding

In Part 1 of the study, the participants and all site personnel, including the Investigator, the site monitor, and the study team must be blinded to study drug treatment, with the exception of the following:

- Any site personnel for whom this information is important to ensure the safety of the participant in the event of a life-threatening medical emergency
- Any site personnel for whom this information is important to ensure the safety of the participant and their fetus in the event of a pregnancy
- Vendors responsible for pharmacovigilance and regulatory personnel at the Sponsor to satisfy serious adverse event (SAE) processing and reporting regulations
- Clinical supply chain personnel at the Sponsor and the vendor
- Unblinded statistician and programmer preparing the final (production) randomization list and unblinded analyses for the data monitoring committee (DMC)
- DMC
- Vendors analyzing PK and biomarker samples
- Vendor conducting the population PK analysis
- IRT vendor
- The Investigator, participant, site personnel, site monitor and study team will become unblinded to a specific participant's treatment assignment, if the participant has disease progression based on IRR or have reached Week 25 and completed End of Part 1 assessments.

9.4.2. Unblinding During Part 1

In exceptional circumstances, emergency unblinding is possible during Part 1 if, in the Investigator's opinion, immediate unblinding of the treatment is necessary for further management of the participant. Participants who are unblinded for emergency will be permanently discontinued from the study.

The Investigator is encouraged to contact the Sponsor or designee and discuss the participant's situation before making the decision to unblind.

Additionally, participants with disease progression confirmed by IRR before completion of Part 1 (ie, Week 25) will be unblinded. Additional information is provided in Section 10.5.

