10.2. End of Study

A participant is considered to have completed the study if s/he has completed Part 1, Part 2, and all Follow-up visits (Safety Follow-up and Disease Follow-up) of the study.

The primary reason for discontinuation or withdrawal of a participant from the study must be determined using the following categories:

- Completed
- Completed (After Early Treatment Discontinuation)
- Progressive Disease by IRR
- Progressive Disease by Investigator Assessment

- Subsequent TGCT Therapy and/or Surgery
- Death
- Withdrawal by Participant (Withdrawal of Consent)
- Lost to Follow-up
- Physician's Decision
- Study Terminated by Sponsor
- Other (Any other reason that in the opinion of the Investigator, would justify removing the participant from the study, based on the best interest of the participant)

If a participant voluntarily withdraws from the study, the Investigator should attempt to contact the participant to determine the reason(s) for withdrawal. No additional study procedures will be performed and no study-related information will be collected after the participant withdraws consent for this study.

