11.6. End-of-Treatment Visit

Part 1 Double-blind

Participants who discontinue study drug in Part 1 should return for an EOT visit within 7 days of the decision to stop study drug and should complete EOT assessments **as outlined in Table 1**. The MRI and ROM assessments will not need to be completed if performed within the previous 30 days.

Part 2 Open Label

Participants who discontinue study drug should return for an EOT visit within 7 days of the decision to stop study drug. At a scheduled clinic visit, if treatment is not given and it becomes evident that open-label study drug will be discontinued, this visit may become the EOT visit.

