11.7. Safety Follow-up Visit

Participants will be required to attend a clinic visit 30 days (± 5 days) after receiving their last dose of study drug or before the start of new TGCT therapy (including radiation or surgery), whichever occurs first. If a participant has been off study drug for more than 30 days at the time of decision to stop treatment, then the Safety Follow-up Visit will be conducted at the EOT visit. The assessments to be conducted at these visits are provided in the relevant schedule of assessments.

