11.8. Disease Follow-up

All participants who discontinue from study treatment for reasons other than radiologically confirmed disease progression or withdrawal of consent will be followed to obtain information about disease status. Participants who discontinue study treatment due to radiologically confirmed disease progression will not need to complete Disease Follow-up. The first disease follow-up will begin 12 weeks (±4 weeks) after the last dose of study drug and an MRI will be required at this visit.

All subsequent disease follow-up will be conducted by telephone every 16 weeks (\pm 4 weeks) thereafter and a review of the participant's medical records for disease status changes will be performed. Disease follow-up will continue for up to 2 years after last dose of study treatment or until radiological progression, start of new subsequent therapy/surgery, or withdrawal of consent. Any SAE occurring during this follow-up period must be reported if assessed as related to study drug by the Investigator.

Information to be collected will include:

- Date of contact
- Status of disease (ie, radiological disease progression, yes/no)
- Date of progression
- Subsequent TGCT therapy and/or surgery (refer to Section 11.9.11)

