11.9.14.4. Reporting Adverse Events

11.9.14.4.1. Reporting of Serious Adverse Events

The written report for SAEs should be submitted on the SAE form provided for this purpose. The SAE report must include the Investigator's opinion as to whether the event is study drug related. If this relationship is determined to be related to study drug, evidence to support this assessment must also be provided.

For clinical study safety reporting purposes, the applicable version of the IB will be used as the reference document to designate event expectedness.

All SAEs that occur within the reporting period, regardless of causality, must be reported by the Investigator to Deciphera via the designee **immediately and no longer than 24 hours** from the point in time when the Investigator becomes aware of the SAE. Serious AEs must be followed until resolution, the condition stabilizes, or the Investigator and Sponsor agree that follow-up is not required. For purposes of regulatory safety monitoring, the Investigator is required to follow the event to resolution and report to the Sponsor the outcome of the event, unless the participant is deemed by the Investigator to be lost to follow-up or the participant completed the safety follow-up period.

If there are suspected unexpected serious adverse reactions (SUSARs) associated with the use of the study drug, the Sponsor or authorized designee will ensure that the appropriate regulatory agencies and all participating investigators are notified on an expedited basis. In addition, the Sponsor or authorized designee will be responsible for notification of SUSARs to the ethics committees. It is the responsibility of the Investigator to promptly notify the local IRB/IEC/ REB of SUSARs according to the institutional policy. An unexpected event is one that is not reported in the IB. Disease progression is not considered an AE. If AEs/SAEs occur in relation to disease progression that are not consistent with the nature and natural progression of the participant's disease, these AEs/SAEs must be reported per AE/SAE reporting requirements in this section.

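### Protocol 9.4.2 takes emergency-unblinded participants out of the study where it should say study drug, which leaves it unclear that their required follow-up continues

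*Protocol*

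**What the plan says.** On emergency unblinding in Part 1, Protocol 9.4.2 says: "Participants who are unblinded for emergency will be permanently discontinued from the study". It gives no procedure for what follows and no cross-reference. For participants unblinded because of confirmed progression, the same section points to 10.5.

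Section 10.1 deals with stopping treatment and 10.2 with leaving the study. Section 10.2 defines completion broadly: "A participant is considered to have completed the study if s/he has completed Part 1, Part 2, and all Follow-up visits". Its list of end-of-study reasons includes completing the study after stopping treatment early, so the two statuses are distinct.

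The follow-up sections are keyed mainly to stopping drug:

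- 11.6: "Participants who discontinue study drug in Part 1 should return for an EOT visit within 7 days of the decision to stop study drug".
- 11.7: "Participants will be required to attend a clinic visit 30 days" (±5 days) after the last dose, or before new TGCT therapy if that comes first.
- 11.8: "All participants who discontinue from study treatment for reasons other than radiologically confirmed disease progression or withdrawal of consent will be followed".
- 11.9.14.4.1: "Serious AEs must be followed until resolution, the condition stabilizes, or the Investigator and Sponsor agree that follow-up is not required".

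None of these makes an exception for emergency unblinding.

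Table 1 footnote p schedules MRIs at End of Part 1, at the End-of-Treatment visit (unless one was done in the previous 30 days) and at the 12-week follow-up. It covers participants who leave the study in Part 1 for reasons other than progression or withdrawn consent.

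**The concern.** Section 9.4.2 uses the word for the wider status. Read with 10.2, being discontinued from the study can be taken to mean that the visits making up the rest of the study no longer apply. The participants concerned have just had an event serious enough to break the blind, so they are the ones for whom the End-of-Treatment visit, the 30-day safety visit and SAE follow-up matter most.

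There is also a smaller efficacy consequence. A site that closes the participant's record may not obtain the Week 25 MRI. SAP 9.10.2 then counts the participant as a non-responder, even after a response at Week 13.

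**Working it through.** **Comparing the texts**

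1. *Does 10.2 end follow-up for everyone who leaves the study?* No. It defines when a participant has completed the study. Its only bar on further procedures and data collection applies after consent is withdrawn.
2. *Do the follow-up sections reach these participants?* Yes. Anyone taken out of the study also stops study drug, so 11.6, 11.7 and 11.8 apply as written. Section 11.8 exempts only radiologically confirmed progression and withdrawn consent. SAE follow-up under 11.9.14.4.1 is tied to the event.
3. *How does the protocol use the phrase elsewhere?* Loosely. Section 7.1 says "Participants randomized to vimseltinib in Part 1 with confirmed disease progression by IRR before Week 25 will discontinue from study", yet 10.5 has the same participants stop treatment and complete End-of-Treatment assessments and Safety Follow-up. Footnote c says "Participants who discontinue study due to confirmed disease progression by IRR will not need to complete Disease Follow-up Visit", an exemption that would be unnecessary if leaving the study ended follow-up by itself. Footnote p requires MRIs from participants described as leaving the study.
4. *What does 9.4.2 itself tell the site?* Nothing beyond discontinuation. Progressors are sent to 10.5, and follow-up of pregnancies is set out in 11.9.14.4.2. Emergency unblinding has no equivalent.

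Steps 1 to 3 show that the intended meaning is probably study drug. Step 4 shows that a reader of 9.4.2 alone would not learn this.

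**Size of the effect on the primary endpoint**

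Inputs from Protocol 12.1 are 80 vimseltinib and 40 placebo participants, response rates of 35% and 5%, a two-sided Fisher's exact test at 5%, and stated power of 98%. Assumed, because the documents give no count: k = 0 to 4 vimseltinib participants lose the Week 25 scan.

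Power = sum over a, b of P(A = a) × P(B = b) × 1[Fisher p ≤ 0.05 for a/80 vs b/40], with A ~ Bin(80 − k, 0.35) and B ~ Bin(40, 0.05).

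- k = 0: 98.32%, which reproduces the stated 98%.
- k = 1: 98.10%
- k = 2: 97.85%
- k = 3: 97.57%
- k = 4: 97.27%

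Expected vimseltinib response rate = 35% × (80 − k)/80, which is 34.6% at k = 1 and 33.25% at k = 4.

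Those figures treat each lost participant as one who would otherwise have responded at 35%. If the four were scanned but, being off drug, responded at 5%, power would be 97.44%. Losing their scans then costs 97.44 − 97.27 = 0.17 points.

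The expected loss in response rate per lost vimseltinib scan runs from 0.05/80 = 0.06 points to 0.35/80 = 0.44 points. On placebo it is 0.05/40 = 0.125 points.

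**Which emergencies could lose the scan**

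SAP 8.3 allows an early termination visit to be mapped to a visit window bounded by midpoints. With 28-day cycles, Cycle 4 Day 1 is Day 85, Cycle 6 Day 1 is Day 141 and Cycle 7 Day 1 is Day 169. The Week 25 window opens at (85 + 169)/2 = Day 127 if imaging visits set it, or (141 + 169)/2 = Day 155 if clinic visits do. An End-of-Treatment scan after that point may serve as Week 25, so the risk is confined to earlier emergencies.

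**The case against.** The strongest reply is that nothing is actually in conflict. Section 10.2 does not say that leaving the study ends follow-up, the follow-up sections cover these participants on their own terms, and the protocol's other uses of the phrase point to the benign meaning. Harm would require a site to act on one sentence and overlook 10.1, 11.6 to 11.8 and Table 1. All of this stands, and it is why the point is one of wording. It does not remove the case for clarifying an operative instruction that will be read under pressure and points nowhere else.

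A reader might infer two stronger things, and the documents support neither.

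- *That 9.4.2 waives follow-up.* No section does so.
- *That 11.5.1 and Table 12, which require the End of Part 1 MRI to be done while blinded, bar a scan after emergency unblinding.* In context that rule orders the planned Week 25 unblinding before entry to Part 2. Section 10.5 already has placebo participants with confirmed progression unblinded and then following the End of Part 1 assessments, so earlier unblinding is not treated as a bar. Footnote p requires the scan, and it remains usable because the primary endpoint is read by blinded independent review.

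**Conclusion.** The point holds as a minor inconsistency in the wording of an operative rule. Follow-up after emergency unblinding is required by the protocol as it stands, but 9.4.2 uses a term that a site could take to end it. The practical risk is to safety and SAE follow-up, and how often it would arise cannot be estimated from the documents.

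The effect on the primary analysis is negligible: about 1 point of power at most for up to four lost vimseltinib scans, and 0.17 points for four if off-drug participants would respond at only 5%. Both figures rest on the assumed count of 0 to 4, the assumed 5% to 35% response range and the protocol's design rates.

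**What to change.** In 9.4.2, replace *the study* with *study drug*. Add one sentence: the End-of-Treatment visit, Safety Follow-up, SAE follow-up, the End of Part 1 (Week 25) MRI under Table 1 footnote p, and Disease Follow-up continue unless consent is withdrawn.

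Optionally, add a note to 11.5.1 and Table 12 that the while-blinded requirement for the MRI concerns the planned Week 25 unblinding.

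The cost is a change of term and one sentence. All of these assessments are already in the protocol, so there are no new visits, scans or data fields, and the SAP does not change.

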9.4.3. Unblinding at End of Part 1 Visit

After completion of the End of Part 1 assessments, participants who wish to continue to the open-label part of this study (Part 2) will be unblinded. Participants randomized to placebo will crossover to receive vimseltinib and participants initially randomized to vimseltinib will continue to receive vimseltinib in Part 2.

9.5. Study Drug Administration

During Part 1, vimseltinib or matching placebo capsules should be administered orally on Day 1 and Day 5 each week at approximately the same time of day.

dose may be taken within 24 hours of the scheduled dosing time (± 1 day window). There should always be at least 24 hours between doses. If the participant missed the scheduled dose, then that dose should be skipped. The next required dose should be taken at the next scheduled time and the participant should not double the dose to make up for an earlier missed dose. Should a participant vomit after dosing, the study drug will not be re-administered.

CCI

After unblinding, participants randomized to vimseltinib in Part 1 and continuing to Part 2 should be instructed to take the same number of capsules per day as they were taking at the End of Part 1 (ie, they will remain at reduced dose if the dose was reduced). Participants randomized to placebo in Part 1 and who choose to continue to Part 2 will initiate vimseltinib 30 mg biw on Crossover Cycle 1 Day 1.

Participants may receive the COVID-19 vaccine or booster while receiving study drug. Participant should schedule the vaccination on the day when dosing with the study drug is not expected. If not possible, the participant should take the study drug at least 2 hours before or after receiving the vaccination or booster.

If a participant receives the COVID-19 vaccination or booster during screening, it is recommended to start study drug at least 7 days after the day of vaccination.

[figure not shown]
If required, study drug may be shipped directly to a participant if they are not able to attend a study visit following the instructions detailed in the Pharmacy Manual.

9.6. Criteria for Dose Interruption and Modification

Study drug may be interrupted and/or modified at the discretion of the Investigator at any time due to AEs. Study drug may also be interrupted for other reasons in consultation with the Sponsor Medical Monitor. Any study drug interruption unrelated to an AE will be limited to 28 days. Upon resumption of study drug following a dose interruption, the Investigator must continue with the participant's original visit schedule calculated from Cycle 1 Day 1. Clinic visits and assessments should continue during dose interruptions.

Each

9.6.1. Dose Interruption and Modification

9.6.2. Dose Reduction Steps for Study Drug

If dose reduction is required, dose reduction steps are as described in Table 8.

Table 8:Dose Reduction Steps for Study Drug

Dose of Study Drug at the Time of Dose Modification	Dose Reduction
30 mg	20 mg
20 mg	14 mg

If a dose reduction of study drug is required, re-escalation of dose may be permitted based on agreement between the Investigator and Sponsor.

A participant will be allowed to have 2 dose level reductions. If more than 2 dose level reductions are required, the study drug will be discontinued.

9.6.3. Dose Interruption and Management of Toxicities

9.6.3.1. Guidelines for Hepatobiliary Lab Elevations

Recommended dose interruption and management of treatment-related hepatobiliary lab elevations are shown in Table 9.

Table 9:Dose Interruption and Management of Treatment-related Hepatobiliary
Laboratory Elevations

Toxicity Grade CTCAE v5.0	Dose Interruption and Management	
Grade 2 ALT and/or AST increase	Continue treatment with study drug	
(>3–5×ULN) and total bilirubin ≤ULN	Check for changes to medications and symptoms	
	Perform confirmation liver enzyme (AST, ALT and ALP) and bilirubin tests within 48-72 hours	
	Repeat liver enzyme tests weekly for 8 weeks to ensure stability	
Grade 2 ALT and/or AST increase	Hold treatment with study drug	
(>3–5×ULN) and total bilirubin	Check for changes to medications and symptoms	
increase up to 2×ULN	Perform confirmation liver enzyme (AST, ALT, and ALP) and bilirubin tests within 48-72 hours	
	Repeat liver enzyme tests weekly	
OR	Study drug may be resumed at 1 dose level reduction once Hy's law has been definitively ruled out, labs resolve to Grade 1 or baseline, after discussion with Sponsor	
Total bilirubin increase up to 2 ×ULN	If ALT/AST/bilirubin continue to increase, or the increased level persists more than 28 days:	
	Discontinue study drug	
	Refer for gastroenterology/hepatology consultation	
	Consider liver ultrasound	

Toxicity Grade CTCAE v5.0	Dose Interruption and Management		
Grade 2 ALT and/or AST increase	Hold treatment with study drug		
(>3–5×ULN) and total bilirubin	Check for changes to medications and symptoms		
increase >2×ULN or INR >1.5 and ALP <2×ULN	Perform confirmation liver enzyme (AST, ALT and ALP), bilirubin, and INR tests within 48-72 hours		
	Refer for gastroenterology/hepatology consultation		
OP	Consider liver ultrasound		
OR	Repeat liver enzyme, bilirubin, and INR tests weekly until resolution to Grade 1 or baseline		
Total bilirubin increase >2×ULN	Study drug may be resumed at 1 dose level reduction once Hy's law has been definitively ruled out, labs resolve to Grade 1 or baseline, after discussion with Sponsor		
	If ALT/AST/bilirubin/INR continue to increase , or the increased level persists more than 28 days:		
	Discontinue study drug		
Grade 3 ALT and/or AST increase	Hold treatment with study drug		
(>5–8×ULN) and total bilirubin \leq ULN	Check for changes to medications and symptoms		
and without clinical symptoms	Perform confirmation liver enzyme (AST, ALT and ALP) and bilirubin tests within 48-72 hours		
	Repeat liver enzyme tests weekly until resolution to Grade 1 or baseline		
	Study drug may be resumed at 1 dose level reduction once labs resolve to Grade 1 or baseline, after discussion with Sponsor		
	If ALT/AST/bilirubin continue to increase, or the increased level persists more than 28 days:		
	Discontinue study drug		
	 Refer for gastroenterology/hepatology consultation 		
	 Perform liver ultrasound 		
Grade 3 ALT and/or AST increase	Discontinue treatment with study drug		
$(>5-8\times ULN)$ and total bilirubin increase	Check for changes to medications and symptoms		
>ULN or INR >1.5 or ALP >2×ULN	Perform confirmation liver enzyme (AST, ALT, and ALP), bilirubin, and INR tests within 48-72 hours		
	Consider gastroenterology/hepatology consultation		
	Perform liver ultrasound		
	Repeat liver enzyme, bilirubin, and INR tests at least twice weekly until resolution to Grade 1 or baseline		
Grade ≥3 ALT and/or AST increase	Discontinue treatment with study drug		
(>8×ULN)	Check for changes to medications and symptoms		
	Repeat liver enzymes and bilirubin tests at least twice weekly until resolution to Grade ≤ 2		

Toxicity Grade CTCAE v5.0	Dose Interruption and Management	
	Refer for gastroenterology/hepatology consultation	
	Perform liver ultrasound	

Abbreviations: ALP=alkaline phosphatase; ALT=alanine aminotransferase; AST=aspartate aminotransferase; CTCAE=Common Terminology Criteria for Adverse Events; INR=international normalized ratio; ULN=upper limit of normal.

Note: Cases of Hy's law must be reported as a serious adverse event and study drug must be discontinued immediately.

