9.6.3.3. Guidelines for Dermatologic Adverse Events

Recommended dose interruption and management of treatment-related skin and subcutaneous disorder and recommendations for management of dry skin are presented in Table 11.

General guidelines for treatment-related dermatologic adverse events:

- Symptoms and signs of hypersensitivity reaction should be monitored at each clinic visit. Refer to Section 9.6.1 for dose interruption guidance
- Use "Rule of 9s" (refer to Appendix 2) to calculate body surface area (BSA) for CTCAE grading

- Participant should be advised to use fragrance-free detergents and soaps, wear sunscreen with sun protection factor ≥30, and moisturize the skin at least once daily, preferably twice daily
- Standardized photos for any Grade ≥2 dermatologic AEs should be submitted to the Sponsor
- A skin biopsy sample (ie, punch biopsy) may be collected locally if a participant experiences a treatment-related dermatologic AE. If collected, the sample will be shipped to a central laboratory and may be analyzed for histopathology and potentially for molecular markers. Specific instructions on collection and shipping of samples will be provided in a separate laboratory manual

Toxicity Grade (CTCAE v5.0)	Maculopapular Rash	Pruritus/Urticaria	Eczema	Dry Skin ^a
Grade 1	 Continue treatment with study drug Treat with mid- to high-potency topical corticosteroid bid 	 Continue treatment with study drug Treat with cooling lotions containing menthol and/or camphor Treat with mid- to high-potency topical corticosteroid bid 	 Continue treatment with study drug Treat with mid- to high-potency topical corticosteroid bid 	 Continue treatment with study drug Apply moisturizing creams/lotions without fragrances/irritants (eg, Oncoderm Body Rx spray; Eucerin original)

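### Table 9 gives conflicting dosing actions for some liver test patterns at normal bilirubin, and the confirmation tests in the milder rows omit INR

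*Protocol*

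**What the plan says.** Table 9 (Protocol Section 9.6.3.1) is introduced as recommended management. Four of its rows matter here.

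- **Grade 2, continue.** ALT/AST >3–5×ULN with bilirubin ≤ULN, and no condition on INR or ALP. Action: "Continue treatment with study drug".
- **Grade 2, hold.** The same ALT/AST band with a bilirubin "increase >2×ULN or INR >1.5 and ALP <2×ULN". Action: hold, with possible resumption at a lower dose after Hy's law is excluded and the Sponsor consulted.
- **Grade 3, hold.** ALT/AST >5–8×ULN with bilirubin ≤ULN "and without clinical symptoms", and no condition on INR or ALP. Action: hold, then "Study drug may be resumed at 1 dose level reduction once labs resolve to Grade 1 or baseline, after discussion with Sponsor".
- **Grade 3, discontinue.** The same band with a bilirubin increase ">ULN or INR >1.5 or ALP >2×ULN". Action: discontinue.

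In the Grade 2 continue row and the Grade 3 hold row the early work-up is "Perform confirmation liver enzyme (AST, ALT and ALP) and bilirubin tests within 48-72 hours". INR is not listed. A further Grade 2 row, for bilirubin up to 2×ULN, has the same test list. The Grade 2 hold row above and the Grade 3 discontinue row do include INR.

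The only table note on action concerns Hy's law. The heading "9.6.1. Dose Interruption and Modification" has no text under it in this copy, although Section 9.6.3.3 points to it: "Refer to Section 9.6.1 for dose interruption guidance".

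In Tables 1 and 2, chemistry is scheduled at C1D15 and C1D15 crossover but coagulation is not. At extension visits (Tables 2 and 3) coagulation is drawn only when clinically indicated.

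**The concern.** A dosing table should give one action for one set of laboratory values. In the discontinue row, INR or ALP alone is a sufficient trigger at normal bilirubin, because the alternatives are joined by *or*. The Grade 3 hold row does not exclude those same values. The two Grade 2 rows have the same fault with INR. Two sites could therefore follow Table 9 faithfully and act differently on identical results: one keeps dosing or rechallenges, the other holds or stops for good.

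The work-up adds to this. INR is the value that moves a Grade 2 participant from continue to hold, yet the continue row does not ask for it. What is at stake is participant safety and consistency between sites.

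**Working it through.** The plan gives no figure to reproduce. The check is a row-by-row enumeration, followed by simple counts.

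**1. Overlaps.** Take bilirubin ≤ULN, and Grade 3 without symptoms. Symptoms play no part in the Grade 2 rows. Cross two INR levels with two ALP levels.

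| ALT/AST | INR | ALP | Rows met |
|---|---|---|---|
| Grade 2 | ≤1.5 | <2×ULN | continue |
| Grade 2 | ≤1.5 | >2×ULN | continue |
| Grade 2 | >1.5 | <2×ULN | **continue and hold** |
| Grade 2 | >1.5 | >2×ULN | continue |
| Grade 3 | ≤1.5 | <2×ULN | hold |
| Grade 3 | ≤1.5 | >2×ULN | **hold and discontinue** |
| Grade 3 | >1.5 | <2×ULN | **hold and discontinue** |
| Grade 3 | >1.5 | >2×ULN | **hold and discontinue** |

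Conflicts: 1 + 3 = 4 of 8. These are table cells, not patients.

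The mixed *and/or* wording can be grouped in other ways. Tying the ALP limit to INR only leaves the count at 4. Strict and-before-or precedence detaches the INR and ALP triggers of the discontinue row from the Grade 3 condition, and the count becomes 3 + 3 = 6. Both named overlaps survive every grouping tried.

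**2. Missing INR.** Three rows omit INR from the 48–72 hour tests: Grade 2 continue, Grade 2 with bilirubin up to 2×ULN, and Grade 3 hold. In the second of these, INR >1.5 with ALP <2×ULN does not change the dosing action, since both matching rows hold. Only the stricter row, however, requires immediate specialist referral and repeat INR.

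**3. Next scheduled INR after an elevation at C1D15.**

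- Part 1 has seven scheduled post-dose chemistry draws: C1D15, Day 1 of Cycles 2 to 6, and End of Part 1. Coagulation accompanies six of them; C1D15 is the exception.
- Nominal gap to C2D1: Day 29 − Day 15 = 14 days.
- With visit windows (C1D15 ±1 day, C2D1 ±7 days): shortest 22 − 16 = 6 days, longest 36 − 14 = 22 days.
- Doses fall on Days 1 and 5 of each week (Section 9.5), so from Day 15 on Days 15, 19, 22, 26, 29 and 33. Before Day 29 that is 4 doses; before Day 22, 2; before Day 36, 6.
- The Day 15 dose falls on the day of the draw itself. With INR on a confirmation draw at Day 17–18, the count would be 1 if the result is back before Day 19 and 2 if it is not. The documents give no turnaround time.

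**4. Likely frequency.** Protocol Section 5.2 reports Grade ≥3 AST increase in 4 (4.6%) of the Phase 1/2 TGCT patients. The denominator is not printed there; 87 is inferred, since 29/87 = 33.3%, 4/87 = 4.6% and 3/87 = 3.4%. The exact 95% interval for 4/87 is 1.3% to 11.4%.

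- 80 vimseltinib participants: 80 × 4/87 = 3.7 (1.0 to 9.1).
- 120, if every placebo participant crosses over: 120 × 4/87 = 5.5 (1.5 to 13.6).

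These are Grade ≥3 AST events, not overlap cases. They include values >8×ULN, which have their own discontinue row. They leave out ALT and any other liver term seen in a single patient. No Grade 2 rate is given.

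**The case against.** **A rule may exist in Section 9.6.1.** The section has no readable text here, and another section cites it for dose interruption guidance, so it evidently has content. This stands. A reader might infer that the protocol has no precedence rule at all; the documents do not support that. What can be said is that Table 9 neither states one nor refers to one.

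**The table is guidance, and the rows escalate.** Each stricter row is the milder pattern plus an added abnormality, so most investigators would take the stricter row. Section 9.6 lets them interrupt for an adverse event whenever they judge it right, and Section 11.9.14.2 allows unscheduled tests. This makes harm less likely. But these provisions permit the safer action without requiring it, and advice to both continue and hold cannot be applied uniformly across about 45 centers.

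**The Sponsor sees these cases.** At Grade 3 this largely holds. Both rows stop drug at once, resumption needs Sponsor discussion, and Section 11.9.14.2 asks sites to try to discuss dosing changes with the Sponsor beforehand, or else to inform it the same day. A reader might infer that a site could rechallenge a Grade 3 case on its own authority; the text does not allow that. Continuing at Grade 2 is not a dosing change, so neither safeguard is triggered there.

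**An unmeasured INR creates no conflict.** True. It means instead that the condition for holding can go unnoticed. Coagulation does accompany most scheduled chemistry draws, so the gap is confined to particular visits.

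**Conclusion.** Both overlaps are real on the face of Table 9: four of eight patterns at bilirubin ≤ULN under the natural reading. The Grade 3 conflict is largely contained. The Grade 2 conflict (INR >1.5, ALP <2×ULN) is the one that matters more, because the continue row has no Sponsor gate and does not call for INR. For an elevation found at C1D15 the next scheduled INR is nominally 14 days away, or about 6–22 days and 2–6 doses once visit windows are allowed for. A fixed comparison of four doses with one would claim more precision than the documents allow.

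Few participants are likely to be affected, and the number is unknown. The Phase 1/2 percentages show only the order of magnitude and set no upper limit, because Section 5.2 lists adverse event terms seen in more than one patient rather than laboratory grades. Section 5.2 also says the transaminase elevations came without bilirubin rises or other signs of liver damage, so no overlap case is documented.

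This is an ambiguity in a safety instruction that should be fixed. A reader might take it to cast doubt on the trial's results. It does not: no efficacy analysis, power figure or type I error is affected. The conclusion is conditional on Section 9.6.1 not already settling which row governs.

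**What to change.** 1. State in Table 9 that when more than one row applies, the most restrictive row governs. If Section 9.6.1 already says so, refer to it in the table.
2. Add INR to the 48–72 hour confirmation tests in the Grade 2 continue row, the Grade 2 row with bilirubin up to 2×ULN, and the Grade 3 hold row.

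The criteria of the Grade 2 continue and Grade 3 hold rows may also be tightened, but that is no substitute for the precedence sentence. It would leave the overlap for Grade 2 with bilirubin up to 2×ULN and INR >1.5. It would also leave the overlaps from the stand-alone bilirubin triggers, which say hold while a Grade 3 or >8×ULN row says discontinue.

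A precedence rule cannot help where no row applies. Symptomatic Grade 3 with bilirubin ≤ULN, INR ≤1.5 and ALP ≤2×ULN fits none and could be closed in the same edit. The Sponsor's hepatic safety experts should confirm the wording.

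Cost: one sentence, and one extra test on a draw already required, taken through the usual ethics and regulatory approval (Section 13.1.3). The downside is a few more INR tests and possibly a few earlier holds or permanent stops, including in participants whose INR is raised for another reason.
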